10.1.3 Sample Size Justification for OS Comparison

For OS, at a two-sided alpha level of 0.019, a total of 419 events are needed to detect a HR of 0.70 with 90% power. Assuming a median OS time for the nivolumab arm (Arm B) of 37.6 months, with a total sample size of 764, in the original protocol it is projected the total study duration is 59 months (15 months for accrual and 44 months for follow up), with a critical boundary hazard ratio of 0.792. With updated enrollment projection in February 2021, it is projected the total study duration (corresponding to the final OS analysis time) is approximately 76.3 months from the first subject's randomization date. All projected OS interim analysis times are updated accordingly. However, all PFS and OS analysis times are driven by the required number of events. The actual analysis times depend on actual enrollment speed and events accrual, thus may be different from projections.

Three formal interim analyses of OS are planned for this study. The first OS interim analysis is planned at the time point of the final PFS analysis, where OS will be tested at 0.0001 level, regardless of the outcome of the final PFS analysis. For instance, if 150 OS events are observed at the time point of the final PFS analysis, then the critical boundary on hazard ratio for the first OS interim is 0.53.

All other formal OS analyses will be conducted when planned number of OS events specified below are observed.

The second OS interim analysis is planned when 230 OS events are observed (55% of the targeted OS events for final analysis, projected to happen 47.9 months from FPFV), and the third OS interim analysis is planned after observing 314 OS events (75% of targeted OS events needed for final analysis, projected to happen 59 months from FPFV). Accounting for the $\alpha = 0.0001$ spent at the first OS interim, the remaining alpha level will be the overall OS alpha level (as described below) minus 0.0001 depending on the ORR and PFS results. If neither ORR nor PFS is significant, the remaining alpha level of 0.0189 ($\alpha=0.019-0.0001$) will be spent on the rest of the OS interim analyses and the final OS analysis. The stopping boundaries for the second OS interim, the third OS interim, and the final OS analyses will be derived based on the actual number of deaths using the O'Brien and Fleming alpha-spending function in software EAST 6.4.1. If the

numbers of events are exactly the same as planned, the critical boundary on hazard ratios for the second, third OS interim analyses and the final OS analysis are 0.646, 0.729, and 0.792, respectively.

If the final ORR analysis is statistically significant, the significance level of 0.001 spent in the ORR analysis will be passed on to the OS analysis. Similarly, if the final PFS analysis is statistically significant, the significance level of 0.03 spent in the PFS analysis will also be passed on to the OS analysis. The alpha spent at the second, third OS interim analyses and the final OS analysis will be adjusted accordingly and the overall alpha level for OS is described at the beginning of [Section 10.1](#).

If there are at least 230 OS events at the time point of the final PFS analysis, then the first planned OS interim analysis and the second planned OS interim analysis (at 230 OS events) will be merged into one OS interim analysis, and will occur at the time point of the final PFS analysis. In this case, there will be no extra spending of two-sided alpha = 0.0001 for the first OS interim analysis, and the stopping boundaries for all OS analyses will be derived based on the actual number of deaths using the O'Brien and Fleming alpha-spending function in software EAST 6.4.1.

If the 419th OS event has not occurred 60 months after randomization of the last participant, then the final OS analysis will take place at that time. In such case, the final analysis boundary will be re-calculated based on the observed final number of events using all remaining alpha for OS.

10.2 Populations for Analyses

For purposes of analysis, the following populations are defined:

Population	Description
All Enrolled Participants	All participants who signed an informed consent form and were registered into the IRT.
Intent-to-Treat (ITT) Population/All Randomized Participants	All participants who were randomized. Participants are grouped within the ITT Population by the treatment to which they were randomized. This is the primary analysis set for baseline characteristics and all efficacy analyses.
ORR Population	All randomized participants who have at least 6 months of follow-up at the time point of the final ORR analysis. A participant's follow-up time is defined here as the time between randomization date and clinical data cut-off date regardless of participant disposition (ie, intent-to-treat principle). This is the primary analysis set for the final ORR analysis, which will occur when approximately the first 480 randomized participants have at least 6 months of follow-up.
Safety Population/All Treated Participants	All participants who receive at least 1 dose (or partial dose) of study drug. Participants are grouped within the Safety population according to the treatment they actually received. This is the analysis set for all safety analyses, as well as, study drug administration.
Biomarker Population	For predictive biomarkers, biomarker population includes all randomized participants who have biomarker data available at baseline. For pharmacodynamic biomarkers, the biomarker population includes all

Population	Description
	randomized participants who have baseline and at least one post-baseline biomarker data available.
All PD-L1 evaluable participants	All randomized participants with quantifiable PD-L1 expression.

[figure not shown]
10.3 Statistical Analyses

A description of the participant population will be included in the statistical output reported, including subgroups of age, gender and race.

Per Protocol Amendment 03, the secondary and exploratory objectives are not applicable. However, exploratory analyses of biomarkers on previously collected samples as per [Section 9.8](#) may be conducted. Any analyses of secondary objectives will be descriptive.

10.3.1 Efficacy Analyses

[figure not shown]
Endpoint	Statistical Analysis Methods
Primary ORR	
ORR is defined as the proportion of participants with a confirmed best overall response of CR or PR in the ITT population by RECIST 1.1 per BICR.
 
A pre-planned analysis of blinded independent central review (BICR)-assessed ORR (using RECIST v 1.1; confirmed at least 4 weeks later) and duration of response is intended for both arms to evaluate the clinical activity of bempegaldesleukin in combination with nivolumab relative to nivolumab.
 
BICR-assessed ORR will be compared using a Cochran-Mantel Haenszel (CMH) two-sided test stratified by the three stratification factors (PD-L1 status, BRAF status, and AJCC M stage) at 0.001 level to control the overall study type I error. An associated odds ratio and 95% and 99.9% confidence interval (CI) will be calculated. The ORR difference between the two treatment arms with its 95% and 99.9% CI will be reported. The ORR and its corresponding 95% exact CI will also be calculated by Clopper-Pearson method for each randomized arm.

Primary Progression-Free Survival	
Progression-free survival (PFS) is defined as the time between the date of randomization and the first date of documented tumor progression using RECIST 1.1 per BICR (see Section 9.1.1.3), or death due to any cause, whichever comes first.
 
A log-rank test stratified by PD-L1 tumor expression status, BRAF mutation status, and M stage will be used to compare PFS between the 2 treatment arms in the ITT Population at 0.03 level. A Cox proportional hazards model with treatment as the single covariate, stratified by the above factors, will be used to estimate the hazard ratio and corresponding 97% CI. The Kaplan-Meier method will be used to further summarize PFS, including PFS curves, medians with corresponding 95% CIs. The PFS rates at 6 and 12 months will also

Endpoint	Statistical Analysis Methods
	
be estimated. In addition, to account for potential non-proportional hazard for PFS, sensitivity analyses will be conducted to compare PFS per BICR between treatment groups using weighted log-rank test. Technical details will be given in the SAP.
 
Participants who do not progress or die will be censored on the date of their last evaluable tumor assessment. Participants who do not have any on-study tumor assessments and do not die will be censored on their date of randomization. Participants who started a new anticancer treatment regimen prior to disease progression will be censored on the date of their last evaluable tumor assessment prior to receiving the new antineoplastic regimen. Participants who are lost to follow up will be censored on the date of their last evaluable tumor assessment.

Primary Overall Survival
	
Overall survival (OS) is defined as the time between the date of randomization and the date of death due to any cause. Participants who do not have a date of death will be censored on the last date for which a participant was known to be alive. OS will be analyzed using the stratified log rank test, Cox proportional hazards model, and Kaplan Meier method, similar to PFS. The OS rates at 12 and 24 months will also be estimated. In addition, similar sensitivity analyses to account for potential non-proportional hazard for OS will also be conducted.


Secondary Clinical Benefit Rate, Duration of Response, Time to Response
	
The clinical benefit rate (CBR), defined as the proportion of participants with CR, PR, or SD per RECIST 1.1 by BICR will be summarized similarly to ORR.
 
Duration of response (DOR) is defined for participants who have a confirmed CR or PR as the date from first documented CR or PR per RECIST 1.1 to the date of the documentation of disease progression by BICR or death due to any cause, whichever is earlier. Participants who do not have disease progression or die will be censored on the date of their last evaluable tumor assessment. The median DOR will be estimated using the Kaplan-Meier method with corresponding 95% CI and range.
 
Time to response (TTR) is defined for participants who had a confirmed CR or PR as the time from the date of randomization to date of first documented CR or PR per RECIST 1.1 as assessed by BICR. The median TTR will be estimated using the Kaplan-Meier method with corresponding 95% CI and range.
 
ORR, PFS, CBR, DoR, TTR assessed by Investigator per RECIST 1.1 will be analyzed similarly to these endpoints assessed by BICR.
 
PFS per BICR, ORR per BICR, and OS in biomarker population (by PD-L1 status) will be analyzed similarly as stated above.

Exploratory PFS2
 	
PFS2 is defined as the time from randomization to objectively documented progression after the next line of therapy, per Investigator assessment, or to death, whichever occurs first. Participants who were alive and without progression after the next line of therapy can be censored at last known alive date. Details on the PFS2 analysis will be described in the SAP.
 

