1 SUMMARY

[figure not shown]
Protocol Title: A Phase 3, Randomized, Open-label Study of NKTR-214 Combined with Nivolumab Versus Nivolumab in Participants with Previously Untreated Unresectable or Metastatic Melanoma

Study Phase: 3

Rationale:

Activation of programmed cell death protein-1 (PD-1) pathway inhibits the cluster of differentiation 28 (CD-28)-mediated upregulation of cytokines, inhibits T cell activation, and inhibits the expansion of previously activated cells. Blockade of the PD-1 pathway has demonstrated clinical activity across multiple tumor types including melanoma. An accumulating body of evidence supports that low levels of tumor infiltrating lymphocytes (TILs) in pretreatment biopsies predict poor clinical response to PD-1 pathway blockade. NKTR-214 (bempegaldesleukin) promotes biased signaling through the IL-2 intermediate affinity receptor (IL-2R $\beta\gamma$) as opposed to the high affinity receptor (IL-2R $\alpha\beta\gamma$) found on regulatory T-cells (Tregs). Bempegaldesleukin increases intra-tumoral CD8+ lymphocytes and natural killer cells as well as the number of PD-1+ CD8+ cells in the tumor and peripheral blood. The biologic activity of bempegaldesleukin makes it a potentially promising immunotherapy to combine with checkpoint inhibitors that target and inhibit the PD-1/PD-L1 pathway.

Per Protocol Amendment 03, the text below related to bempegaldesleukin is not applicable. The current study aims to demonstrate that treatment with bempegaldesleukin in combination with nivolumab will be efficacious in participants with unresectable or metastatic melanoma that is previously untreated.

The addition of bempegaldesleukin to nivolumab did not result in a statistically significant improvement in PFS (HR 1.09, 97% CI, 0.88-1.35) or ORR compared to nivolumab monotherapy as assessed by Blinded Independent Central Review (BICR), and the significance threshold for OS was also not crossed at the combined first and second OS analyses. Furthermore, there was added toxicity with bempegaldesleukin plus nivolumab compared to nivolumab monotherapy including

a higher incidence of drug-related adverse events (AEs), drug-related serious adverse events (SAEs) and drug-related AEs leading to study treatment discontinuation.

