5.4.4 Rationale for Choice of Endpoints

CA045001 will use the primary endpoints of ORR, PFS, and OS. ORR and PFS will be assessed per RECIST 1.1 by BICR. ORR will further be described by the durability and depth of responses, as those aspects are important characterizations of responses with immune-oncology treatments.

In the current melanoma clinical environment where multiple approved agents (ipilimumab and BRAF inhibitors) are available to treat the patients who progress on nivolumab with or without NKTR, PFS will not be confounded by subsequent therapy.

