8 DISCONTINUATION AND RESUMPTION CRITERIA

8.1 Discontinuation from Study Treatment

Participants **MUST** discontinue investigational product (and non-investigational product at the discretion of the Investigator) for any of the following reasons:

- Participant's request to stop study treatment. Participants who request to discontinue study treatment will remain in the study and must continue to be followed for protocol specified follow-up procedures. The only exception to this is when a participant specifically withdraws consent for any further contact with him/her or persons previously authorized by participant to provide this information
- Any clinical adverse event (AE), laboratory abnormality or intercurrent illness which, in the opinion of the Investigator, indicates that continued participation in the study is not in the best interest of the participant
- Termination of the study by Bristol-Myers Squibb (BMS)
- Loss of ability to freely provide consent through imprisonment or involuntarily incarceration for treatment of either a psychiatric or physical (eg, infectious disease) illness. (Note: Under specific circumstances and only in countries where local regulations permit, a participant who has been imprisoned may be permitted to continue as a participant. Strict conditions apply and BMS approval is required.)
- Disease progression in the absence of clinical benefit as determined by the Investigator.

- Clinical disease progression in the absence of radiologically confirmed progression by RECIST 1.1
- See Section 8.1.1 for Nivolumab and Bempegaldesleukin Discontinuation Criteria.
- Noncompliance of the participant with protocol-mandated procedures based on the judgment and agreement of both the Investigator and Sponsor

If a participant has not progressed following discontinuation of study drug(s), every effort should be made to continue to obtain radiographic tumor assessments until Investigator confirmed progression.

A participant may also be withdrawn from investigational product/study by the Sponsor, Regulatory Authorities, or Institutional Review Boards (IRBs)/ Independent Ethics Committees (IECs).

Participants may choose to discontinue the study at any time, for any reason, and without prejudice to further treatment.

Refer to the Schedule of Activities for data to be collected at the time of treatment discontinuation and follow-up and for any further evaluations that can be completed.

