9.1.1.3 BICR Confirmation of Progression

Per Protocol Amendment 03, BICR will be discontinued and all study treatment decisions will be based on the Investigator's assessment of tumor images.

Not applicable per Protocol Amendment 03. Sites should submit all scans to the imaging core lab on a rolling basis, throughout the duration of the study. BICR of scans will occur on a rolling basis, blinded to treatment arm, clinical data, and Investigator assessment of submitted scans. When progression per RECIST 1.1 criteria is assessed by the Investigator, the site will inform the imaging core lab, so that the BICR assessment of progression can be performed. The BICR review will be completed and the results provided to the site as specified in imaging vendor documents, provided there are no pending imaging queries to the site. All details on the timelines and associated process requirements will be outlined in the Imaging Manual.

Not applicable per Protocol Amendment 03. Participants whose progression is not confirmed by the BICR will be required to continue tumor assessments (if clinically feasible) according to

the protocol-specified schedule, or sooner if clinically indicated. Also, if participants discontinue treatment without radiographic progression, tumor assessments will continue according to the protocol specified schedule, as noted in [Section 2](#), until progression has been confirmed by BICR.

[figure not shown]
All study treatment decisions will be based on the Investigator's assessment of tumor images and not on the BICR assessment. The BICR assessment of progression is only relevant for determining when tumor assessments for a given participant are no longer required to be submitted to the imaging vendor.

[figure not shown]

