2.3 Response Assessment

2.3.1 Evaluation of Best Overall Response

The best overall response is the best response recorded from the start of the study treatment until disease progression or the last response recorded, taking into account any requirement for confirmation and censoring rules regarding subsequent therapy. The patient's best overall response assignment will depend on the findings of both target and non-target disease and will also take into consideration the appearance of new lesions. Furthermore, depending on the nature of the study and the protocol requirements, it may also require confirmatory measurement.

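### Does censoring primary PFS, but not duration of response, at new anticancer therapy conflict with Section 5.4.4 or undermine either endpoint?

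*Combined protocol and SAP*

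**What the plan says.** Section 5.4.4 explains why PFS is a primary endpoint. It notes that other approved agents are available for patients who progress on nivolumab, with or without bempegaldesleukin, and concludes that "PFS will not be confounded by subsequent therapy".

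In Section 10.3.1 the primary PFS event is BICR progression or death. For therapy begun earlier the row says: "Participants who started a new anticancer treatment regimen prior to disease progression will be censored on the date of their last evaluable tumor assessment", meaning the last one before the new regimen.

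The DOR row of Section 10.3.1 uses the same end event in confirmed responders. Its only censoring sentence is: "Participants who do not have disease progression or die will be censored on the date of their last evaluable tumor assessment". It does not mention new therapy and does not refer back to the PFS row. Appendix 9, Section 2.3.1, determines best overall response "taking into account any requirement for confirmation and censoring rules regarding subsequent therapy", but does not mention DOR.

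Three further places matter:
- Section 9.1.1.3 bases treatment decisions on the Investigator's "assessment of tumor images and not on the BICR assessment".
- The same section, in the text in force before Amendment 03, has the site notify the core lab of Investigator progression "so that the BICR assessment of progression can be performed", and has scanning continue where BICR does not confirm it.
- Section 8.1 lists "Clinical disease progression in the absence of radiologically confirmed progression by RECIST 1.1" among the reasons to stop treatment.

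**The concern.** The PFS event is a BICR call, but treatment follows the Investigator. In an open-label trial a participant can therefore start another regimen before BICR progression, after an Investigator-called progression, clinical progression or toxicity. Censoring such a participant assumes that the switch says nothing about imminent BICR progression. If it does, and switching differs by arm, the hazard ratio is biased. The Summary reports a higher incidence of "drug-related AEs leading to study treatment discontinuation" with the combination, which suggests a possible imbalance. Read alone, the 5.4.4 sentence seems to deny that any of this can happen.

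The second worry is coherence. DOR and PFS come from the same BICR reads. If one censors at new therapy and the other does not, the same responder can leave the PFS analysis without an event and then contribute a later DOR event. At stake would be how the primary hazard ratio is interpreted and whether the durability figures can be compared with it.

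**Working it through.** **1. Do 5.4.4 and 10.3.1 conflict?** The subject of the 5.4.4 sentence is treatment for patients who progress. Therapy given after the PFS event cannot alter PFS. Section 10.3.1 covers the other case, therapy started before the event, and says openly how it is handled. A gap remains for therapy started after Investigator progression but before BICR progression. The 10.3.1 rule covers that too, and the triggered BICR read and continued scanning limit how often it arises.

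**2. Do PFS and DOR differ as written?** Table 2-2 gives scans every 9 weeks to Week 54, so at Weeks 9, 18, 27, 36, 45 and 54. Take a response first seen at Week 9 and later confirmed, new therapy at Week 50, and BICR progression at Week 54 (invented dates).
- PFS: censored at Week 45.
- DOR as written: event, 54 − 9 = 45 weeks.
- DOR under the PFS rule: censored at 45 − 9 = 36 weeks.

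The difference is real and needs no assumed rate.

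**3. How large could the DOR difference be?** The documents give no rates. A simulation of 400,000 responders assumed exponential DOR, uniform follow-up of 6–36 months, and 10% or 20% of progressions preceded by a switch, with censoring 63 or 126 days earlier.

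| Assumed 12-month rate, share switching | 12 months: row vs PFS rule | 24 months: row vs PFS rule |
|---|---|---|
| 70%, 10% | 70.1 vs 72.4% | 49.0 vs 52.3% |
| 70%, 20% | 70.0 vs 74.8% | 49.1 vs 56.0% |
| 80%, 10% | 80.1 vs 81.8% | 64.0 vs 66.7% |
| 80%, 20% | 79.9 vs 83.4% | 64.0 vs 69.7% |

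The gaps are 1.7–4.8 points at 12 months and 2.7–6.9 at 24 months.

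**4. Does the PFS rule threaten the PFS result?** The plan's own figures reproduce first.
- Events = 4(z₀.₉₈₅ + z₀.₉₀)² / (ln 0.7)² = 4(2.170 + 1.282)² / 0.1272 = 374.7, so 375.
- Critical HR = exp(−2 × 2.170 / √375) = exp(−0.224) = 0.799.

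The reported HR is 1.09. To have hidden a significant benefit, the rule would have had to inflate the HR by 1.09 / 0.799 = 1.36. A large-sample simulation used the plan's control curve (63/52/46/37% at 3/6/9/18 months), 24 months of follow-up, and switchers censored 2.1 months before progression. Switching shares are experimental/control.

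| Switching | True HR 0.70 | True HR 1.0 |
|---|---|---|
| 0/0 | 0.695 | 1.008 |
| 10/10% | 0.691 | 0.984 |
| 5/15% | 0.772 | 1.090 |
| 5/20% | 0.804 | 1.165 |
| 15/5% | 0.629 | 0.900 |

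Equal switching hardly moves the HR. The largest upward factor is 0.804 / 0.695 = 1.165 / 1.008 = 1.16, well short of 1.36. If switching were instead more common in the combination arm, as the toxicity figures might suggest, the observed HR would be too low, and the underlying effect would be less favourable than 1.09.

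**The case for a change.** The best case for a change runs as follows. The 5.4.4 wording is too absolute for a BICR endpoint when Investigators decide treatment. The only PFS sensitivity analysis named in 10.3.1 is the weighted log-rank test, which addresses non-proportional hazards and not informative censoring. Investigator-assessed PFS counts an Investigator-called progression as an event, but it is analysed in the same way, so a switch after clinical progression or toxicity is censored in both versions. DOR is not incidental either, since 10.3.1 pairs it with the primary ORR. The remedy would be cheap: two sentences, a table of censoring reasons by arm, and one descriptive run.

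The textual facts stand, and so does the silence of the DOR row. The rest carries less weight:
- Stopping a drug for toxicity is not the same as starting another anticancer regimen. Section 7.1.2 let Arm A nivolumab continue when bempegaldesleukin was stopped, and Section 8.1.1 allowed single-agent continuation with approval. Switches for toxicity alone may not be informative at all.
- Section 10.3.3.3 leaves PFS sensitivity analyses to the SAP, and Section 10 leaves detailed methods there too. That separate SAP is not in the document reviewed, so an omission cannot be inferred.
- Ignoring new therapy for DOR and censoring at it are both recognised choices that answer slightly different questions. A report that names the one used leaves no ambiguity.

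**Conclusion.** No change to the plan is called for. Section 5.4.4 and the PFS rule address therapy after and before progression respectively; narrower wording in a rationale section would alter no result. The primary censoring rule is explicit and acceptable.

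The DOR row leaves out a detail that an analyst settles by choosing, and naming, one of two defensible conventions. Under the assumptions in step 3 the choice moves a 12-month DOR rate by about 2 to 5 points. DOR carries no alpha, and Section 10.3 as amended makes any analysis of secondary objectives descriptive.

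The final PFS analysis is complete (database lock 01-Feb-2022; HR 1.09, 97% CI 0.88–1.35), and no event count, power, boundary or decision depends on this point. The switching rates, their informativeness and the lags are assumptions throughout, so the simulated figures only indicate scale. The argument that 5.4.4 and 10.3.1 are compatible rests on the text and needs none of them.
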